### **3.1 Object of Study**

1. **Source of the study subjects and the sampling methods:** The study subjects will be selected from the respiratory department of a tertiary hospital in Xiamen, Fujian Province, and a community health service center in Tong'an District, Xiamen. The sampling method is convenience sampling.
2. **Inclusion criteria for the study subjects:**
  - Diagnosed as COPD by a physician.
  - $\text{SpO}_2 < 88\%$  or  $\text{PaO}_2 < 60\text{mmHg}$ .
  - Diagnosed with MCI.
  - Have a home oxygen concentrator.
  - No communication barriers.
3. **Exclusion criteria for the study subject:**
  - Complicated with asthma or lung cancer.
  - Long - term home oxygen therapy time  $\geq 15\text{h/d}$ .
  - Participated in similar interventions.
4. **Samplesize estimation:** The sample size is calculated using the formula for comparing two - sample rates. Referring to the literature, the oxygen therapy compliance rate is 20%, and it is expected to increase by 40% after intervention. With a significance level of 0.05 and a Type II error probability of 0.1, 32 cases are required for each of the intervention group and the control group. Considering a 20% dropout rate, the final sample size is determined to be 39 cases per group, with a total of 78 cases.

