### **3.3 Data Processing and Statistical Analysis**

1. After the data collection is completed, SPSS 20.0 software is used for statistical analysis.
2. The description of general demographic data and clinical data: Count data are described by frequency and percentage; measurement data are described by median.
3. Comparison of general demographic data and clinical data between the two groups of research subjects: Rank - sum test and X test are used.
4. Comparison of the total scores of long - term home oxygen therapy beliefs at each time point between the two groups of research subjects: Repeated - measures analysis of variance is used.
5. Comparison of the scores of each dimension of long - term home oxygen therapy beliefs, long - term home oxygen therapy behavior scores, and average daily oxygen inhalation time at each time point between the two groups of research subjects: Generalized linear mixed - effect model is used for analysis.
6. Comparison between groups of the total scores and scores of each dimension of long - term home oxygen therapy beliefs, long - term home oxygen therapy behavior scores, and average daily oxygen inhalation time at different time points of the two groups of research subjects: If it conforms to the normal

---

distribution, an independent - sample t - test is used; if it does not conform to the normal distribution, a two - independent - sample rank - sum test is used.

7. Comparison within groups of the total scores and scores of each dimension of long - term home oxygen therapy beliefs, long - term home oxygen therapy behavior scores, and average daily oxygen inhalation time at different time points of the two groups of research subjects: If it conforms to the normal distribution, a paired t - test is used; if it does not conform to the normal distribution, a paired rank - sum test is used.
8. Comparison of the differences in the scores of the Montreal Cognitive Assessment Scale, Mini - Mental State Examination, Geriatric Depression Scale, and Self - rating Anxiety Scale between the intervention group and the control group: An independent - sample t - test is used.

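### Unadjusted between-group tests in section 3.3 items 6 and 8, with no stated deciding analysis alongside items 4-5, should give way to one baseline-adjusted model per outcome with a named deciding contrast

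*Combined protocol and SAP*

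**What the plan says.** All of the relevant text is in the combined protocol and SAP.

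- **Section 3.3 item 4** (belief total, compared between groups over time): "Repeated - measures analysis of variance is used".
- **Section 3.3 item 5** (belief dimensions, behaviour score, daily oxygen hours): "Generalized linear mixed - effect model is used for analysis". Neither item names fixed or random terms, and item 5 gives no distribution or link.
- **Section 3.3 item 6** compares every outcome in items 4 and 5 between groups again. If the data are normal, "an independent - sample t - test is used; if it does not conform to the normal distribution", a rank-sum test takes its place. No normality rule and no list of time points is given.
- **Section 3.3 item 7** compares time points within each group. Under normality, "a paired t - test is used".
- **Section 3.3 item 8** begins "Comparison of the differences in the scores of the Montreal Cognitive Assessment Scale", adds three further scales, and specifies an independent-sample t-test. The wording could mean follow-up scores or change scores.
- **Section 3.1** excludes patients whose "Long - term home oxygen therapy time" is already 15 h/d or more. It sizes the trial on a rate: "the oxygen therapy compliance rate is 20%, and it is expected to increase by 40% after intervention".

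**The concern.** There are two linked problems.

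First, each item 6 outcome has two between-group results, one from items 4-5 and one from item 6. They can disagree, and no rule says which one counts. Because the models in items 4-5 have no terms, baseline could be a covariate, one of the repeated time points, or absent.

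Second, the tests that are fully described (items 6 and 8) ignore the baseline score or, at best for item 8, subtract it. Under random allocation this is a loss of precision. It also leaves any chance baseline imbalance in the estimate. With about 31 evaluable patients per group, a chance imbalance of some size is common. The outcomes affected are those closest to objective 2, self-management and compliance.

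**Working it through.** **Sample size.** The plan's own figure reproduces. With rates 0.20 and 0.60, mean 0.40, two-sided alpha 0.05 and power 0.90: 2 × 0.40 × 0.60 × 10.507 / 0.40² = 31.5, so 32 per group. Then 32 × 1.2 = 38.4, so 39. With 20% loss, 39 × 0.8 = 31.2, so 31 evaluable per group are used below. This calculation concerns a rate. The documents give no SD, correlation or expected effect for any score, so the correlation r and the effect in SD units are assumptions, shown as ranges from linear models with equal SDs at baseline and follow-up.

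**Variance of the group difference**, in units of 2σ²/n:

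- follow-up-only: 1
- change score, or a baseline-to-follow-up group-by-time contrast: 2(1 − r)
- baseline-adjusted: 1 − r²

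The cut from adjustment is therefore r² against follow-up-only and 1 − (1 + r)/2 against change.

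| | r = 0.3 | r = 0.5 | r = 0.7 |
|---|---|---|---|
| Cut against follow-up-only | 9% | 25% | 49% |
| Cut against change | 35% | 25% | 15% |
| Power at 0.6 SD, follow-up-only | 64% | 64% | 64% |
| Power at 0.6 SD, change | 50% | 64% | 85% |
| Power at 0.6 SD, adjusted | 67% | 76% | 90% |
| 95% CI half-width, follow-up-only (SD) | 0.51 | 0.51 | 0.51 |
| 95% CI half-width, adjusted (SD) | 0.48 | 0.44 | 0.36 |

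**Dependence on the effect**, at r = 0.5, follow-up-only to adjusted: 34% to about 43% at 0.4 SD; 64% to 76% at 0.6 SD; 87% to 94% at 0.8 SD; 98.9% to 99.8% at 1.1 SD.

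**Chance imbalance.** The SD of the baseline difference is √(2/31) = 0.254 SD, so a difference beyond 0.25 SD in either direction occurs in about 32% of randomised trials of this size. It shifts a follow-up-only estimate by r × 0.25 = 0.08 / 0.13 / 0.18 SD, and a change estimate by (1 − r) × 0.25 = 0.18 / 0.13 / 0.08 SD in the opposite direction.

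**Oxygen hours.** Excluding patients at 15 h/d or more narrows the baseline distribution and lowers r. As an illustration only, removing the top 20% of a normal distribution leaves variance 0.583. The correlation becomes r√0.583 / √(0.583r² + 1 − r²) = 0.23 / 0.40 / 0.60, and the cut against follow-up-only falls to 5% / 16% / 36%.

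**Cost if r = 0.** The variance factor is 1 + 1/(62 − 4) = 1.017. Power at 0.6 SD goes from 64% to 63%.

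**Type I error.** In simulation with no effect, the t-tests and ANCOVA each reject at 4.9% to 5.1% per test.

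**The case against.** **The order may be deliberate.** Items 4-5, then 6, then 7 look like an overall model followed by simple between- and within-group comparisons. That is plausible, and one sentence assigning roles would answer the precedence question without a new model. But the text does not say so, items 4-5 are themselves framed as comparisons at each time point, and the sentence would not supply model terms or make items 6 and 8 more precise.

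**The gain is conditional.** This stands in full. It needs a pre-intervention measurement, which item 7 and the 15 h/d exclusion make likely but not certain; for the item 8 scales it is less clear still, since section 3.2 describes only MoCA. It needs r above zero. Item 5 may already include baseline, in which case nothing is gained over that model.

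**At the plan's own effect the power gain is negligible.** If compliance is a cut on normally distributed hours, 20% to 60% is z(0.6) − z(0.2) = 1.1 SD, where power is already 98.9%. This is fair for power, though intervals would still narrow. The conversion also does not fit with the truncation illustration: one keeps 20% of controls above the cut, the other removes the top 20% at baseline. The two figures are separate illustrations, not one description of this trial.

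**Stronger readings that the documents do not support.** A reader might infer that the t-tests are invalid; under random allocation they are not. A reader might infer that adopting one model settles which result counts. A model with group-by-visit still yields one contrast per visit, so a visit or averaged contrast must also be named. A reader might infer that adjustment cures a non-random comparison. It does not, and the available text describes no allocation step.

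**Conclusion.** The point holds as an inexpensive improvement, not as a flaw that invalidates the analysis. The documentary part needs no assumption: the item 6 outcomes have two between-group analyses, the models have no stated terms, and neither is designated as deciding. The statistical part is that the unadjusted tests in items 6 and 8 are less precise than a baseline-adjusted analysis wherever baseline was measured and is correlated with follow-up.

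Its size depends on assumed correlations and effects. It is material for moderate effects, small when r is low, and close to nil in power terms above 1 SD. It is smaller for oxygen hours than for the other outcomes at the same underlying correlation. The linear-model figures do not carry over directly to the 13-item behaviour count.

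**What to change.** For each outcome with a pre-intervention measurement:

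1. Make the deciding analysis a model of follow-up scores with baseline score, group, visit and group-by-visit. Use the item 5 mixed model with these terms, and extend it to belief total in place of the item 4 ANOVA. State the distribution and link, in particular for the behaviour count.
2. Where there is a single follow-up, including MoCA if that applies, use ANCOVA on the follow-up score.
3. Name the one visit or averaged contrast that decides, and report the adjusted difference with its 95% CI.
4. Label the item 6 and item 8 tests as supportive, and say whether item 8 means follow-up or change scores.
5. State which outcomes are measured before the intervention.

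The wording should be fixed before group results are examined. The cost is SAP text, slightly more modelling, and about 2% more variance if the baseline correlation is zero; no patients are added. The change does not choose a primary outcome, does not deal with multiplicity across the seven item 6 scores (belief total, four dimensions, behaviour, hours), and does not remove bias from non-random allocation.

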### 3.2 Research Tool

(1) The execution of LTHOT was assessed using a self-designed Long-Term Home Oxygen Therapy Behavior Survey. Given that improper operational skills can affect the effectiveness of long-term home oxygen therapy, the survey primarily includes four dimensions: adherence to home oxygen therapy, cleaning and disinfection, safe oxygen use, and self-monitoring, with a total of 13 items. Each item has two response options: "Yes" and "No," where "Yes" indicates the behavior was performed, and "No" indicates it was not. A score of 1 is awarded for "Yes," and 0 for "No." The higher the total score, the better the patient's long-term home oxygen therapy behavior. The average daily oxygen use time was self-reported by the patient.

(2) LTHOT Health Belief was assessed using the Long-Term Home Oxygen Therapy Health Belief Questionnaire designed by Yan, J. The questionnaire consists of four dimensions and 26 items. Scores are based on the individual's understanding of their ability to engage in long-term home oxygen therapy behaviors. The total score ranges from 0 to 104, with higher scores indicating a higher level of perceived ability to perform long-term home oxygen therapy health behaviors.

(3) Activity of Daily Living (ADL): Daily living ability was assessed using the Activity of Daily Living scale, with a total score range of 14-56 points. A higher score indicates poorer functional ability. A total score greater than 16 points indicates varying degrees of functional impairment, while a score of 22 points or higher indicates significant functional impairment. If the score for any single item exceeds 3 points, or if two or more items score over 3 points, this suggests significant functional impairment.

(4) Ventilation Function Indicators: These include blood oxygen saturation (SpO2), arterial carbon dioxide partial pressure (PaCO2), arterial oxygen partial

---

pressure (PaO2), pH, lung function (FEV1%), dyspnea score, and 6-minute walk distance (6MWD).

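### Daily oxygen hours decide who enters and are then tested for within-group change; if the screening report is also the baseline, regression to the mean can produce a false rise

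*Combined protocol and SAP*

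**What the plan says.** - **Entry rule.** Section 3.1 item 3 lists "Long - term home oxygen therapy time" of 15 h/d or more as an exclusion. Every enrolled patient is therefore below 15 h/d on whatever value was used at screening. The section does not say how that value is obtained.
- **Measurement.** Section 3.2 item 1 gives the only source of daily hours in the plan: "The average daily oxygen use time was self-reported by the patient". No reliability or standard deviation is given.
- **Within-group test.** Section 3.3 item 7 covers, among other scores, "average daily oxygen inhalation time at different time points of the two groups of research subjects", compared within each group. The method is "If it conforms to the normal distribution, a paired t - test is used", with a paired rank-sum test otherwise. Item 7 states no direction and is not labelled descriptive.
- **Between-group tests.** The same variable is compared between groups in item 5 ("Generalized linear mixed - effect model is used for analysis") and in item 6 (independent-sample t-test or rank-sum test at each time point).
- **Baseline.** No section says whether the report used for eligibility is also the analysed baseline, or whether hours are asked again after screening.

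**The concern.** A self-report carries error. A one-sided cut on such a variable keeps some patients whose report happened to fall below their usual level, and drops some whose report happened to fall above it. The next report from those kept is higher on average even if their use has not changed. A paired test takes zero expected change as its null hypothesis. For daily hours that null would be wrong in a known direction, upward, whenever the baseline value is the one on which patients were selected.

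A significant rise in the intervention group could then be read as an effect of the education, and a significant rise in the control group as a benefit of usual care. Neither need be true. The artefact comes from the cut-off on the outcome itself and would occur in fully stable patients.

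**Working it through.** **1. The plan's own figure.** The sample size uses "the oxygen therapy compliance rate is 20%, and it is expected to increase by 40% after intervention" and "With a significance level of 0.05 and a Type II error probability of 0.1". Reading the increase as 40 percentage points, p1 = 0.20, p2 = 0.60 and their mean is 0.40:

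n = 2 × 0.40 × 0.60 × (1.960 + 1.282)² / 0.40² = 31.5, so 32 per group.

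This agrees with the plan. The final 39 per group is 32 × 1.2 = 38.4, rounded up. After 20% dropout, 39 × 0.8 = 31.2, so about 31 patients per group would be analysed. The calculation compares two groups on a rate and does not depend on item 7. It is used here only for the group sizes.

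**2. Expected change with no true effect.** Assume:
- reports are bivariate normal with equal variance at the two visits;
- true use is unchanged;
- the correlation between two reports is r;
- a share q of unselected patients reports 15 h/d or more;
- the screening report is the baseline.

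With c defined by 1 − Φ(c) = q,

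expected rise = (1 − r) × φ(c)/Φ(c), in SD units.

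For q = 0.20, c = 0.8416 and φ(c)/Φ(c) = 0.35. The rise is 0.035 SD at r = 0.9, 0.105 SD at r = 0.7 and 0.175 SD at r = 0.5. With an assumed SD of 4 h that is about 0.14, 0.4 and 0.7 h/d.

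**3. Chance that the paired t-test declares a significant rise in one group.** Simulation under the same assumptions, two-sided 5% test, upward rejections only (nominal 2.5%). Each cell gives n = 32, then n = 39.

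| Share q at 15 h/d or more | r = 0.9 | r = 0.7 | r = 0.5 |
|---|---|---|---|
| 5% | 3.5%, 3.5% | 4.1%, 4.4% | 4.5%, 4.9% |
| 20% | 6.3%, 7.1% | 11.6%, 13.7% | 17.2%, 20.0% |
| 40% | 12.5%, 14.3% | 30.1%, 35.3% | 48.1%, 56.4% |

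With 31 patients and q = 20% the rates are about 6%, 11% and 17%. The paired rank-sum test is inflated to a similar degree, so the non-normal branch of item 7 gives no protection.

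**4. Two checks on where the artefact stops.**
- *Separate baseline.* If the analysed baseline is a second report with independent error, taken after screening, the upward rate returns to 2.5% (q = 20%, r = 0.8 and 0.5, n = 32).
- *Between-group test at follow-up, same selection rule in both groups.* The two-sided rejection rate is 5.0% at r = 0.7 and 5.2% at r = 0.5 (q = 20%, n = 32), which is nominal.

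**The case against.** The strongest case on the other side has four parts.

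**The comparative analyses are sound on this point.** Items 5 and 6 compare hours between groups, and nothing says that item 7 decides efficacy. This stands, provided both groups are selected by the same rule from comparable patients; the text describes no random allocation. A reader might infer from "it is expected to increase by 40% after intervention" that the plan rests its claim on a before-after rise. The documents do not support that: the phrase sits inside a formula for comparing two groups' rates. What remains is that item 7 is a planned significance test with no stated subordinate role.

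**The premise comes from silence.** The artefact needs the screening value to be the baseline, or to share its error, and the plan does not say so. This also stands and makes the point conditional. A reader might infer that the null of item 7 is certainly false, or that a significant rise is to be expected. Neither follows.

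**The size is assumed.** The SD, r and q are not in the documents. The 20% compliance rate is a convenient value for q, but the sample-size text neither defines compliance as 15 h/d or more nor says that the rate describes unselected patients. The variable is an average rather than a single day's reading, which favours a higher r. At r = 0.5 with an SD of 4 h, the implied error SD is 4 × √0.5 = 2.8 h/d, which no section supports. Hence the range over q and r. The direction does not depend on these values.

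**Changing the test for hours alone is selective.** Item 7 keeps the same tests for belief and behaviour scores. But those scores are not entry criteria, so this direct selection argument applies only to hours.

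**Conclusion.** The point holds conditionally. If the analysed baseline is the screening report or shares its error, item 7 is biased towards a rise in daily hours in either group. The upward false-positive rate is then about 3-5%, 6-20% or 12-56% for a share of 5%, 20% or 40% at 15 h/d or more, against 2.5%. These figures assume normal reports, r from 0.5 to 0.9, 31 to 39 patients per group and no true change. If hours are reported afresh after screening with independent error, the artefact disappears. At the mild end (q = 5%, or r = 0.9 with q = 20%) the inflation is small.

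The finding does not extend to items 5 and 6, and it does not show that the trial's conclusion will be wrong. It concerns one planned test whose p-value should not be offered as evidence of effect. It is a cheap improvement of minor to moderate priority.

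**What to change.** **Main change (section 3.3 item 7).** For average daily oxygen time, replace the paired significance test with a description of each group's mean or median change and its 95% confidence interval. State that evidence of an effect on hours comes only from the between-group comparison in items 5 and 6. The sentence matters because the interval for within-group change carries the same possible upward shift as the test.

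**Optional addition (sections 3.1 and 3.2).** Keep the screening report of hours for eligibility only. Ask the same question again at the baseline visit, before the education starts, and use that second report as the analysed baseline. This removes the expected artefact only if reports are about equally correlated across visits. If a separate baseline report is already intended, one sentence saying so would be enough for this part.

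**Cost.** One sentence in section 3.3 and, if the option is taken, one repeated question. No extra patients are needed. There would be no within-group p-value for hours. Some patients would report 15 h/d or more on the second report; they would stay in the analysis.

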### **3.4 The Project Involves the Implementation Plan of the Ethical Par**

1. **Voluntary Principle:** Ensure informed consent. Before participating in the study, patients are informed of the purpose, content, and procedures of the study. Patients can freely withdraw from the study during the process, and their relevant rights will not be damaged.
2. **Confidentiality Principle:** Seek the opinions of patients on the confidentiality of the research content according to the research questions. Adhere to the confidentiality principle for issues involving participants' privacy and personal safety.
3. **Beneficence and Non - maleficence Principle:** This study has no potential harm to the physical and mental health of patients. On the contrary, the intervention may be beneficial to the implementation of long - term home oxygen therapy and treatment outcomes of patients.

4. **Justice Principle:** Treat all research subjects equally. Whether in the control group or the intervention group, strictly follow the research design plan to conduct the research rigorously and fairly.
